Non-Interventional Study (NIS) Protocol

Document Number:	c39368586-02
BI Study Number:	1245-0228
BI Investigational Product(s):	Jardiance® (empagliflozin)
Title:	Comparative cardiovascular and renal effectiveness and safety of Empagliflozin and other SGLT2i in patients with type 2 diabetes (T2D) with and without baseline kidney disease in the United States
Brief lay title:	Evaluating comparative effectiveness of empagliflozin in patients with type 2 diabetes with and without chronic kidney disease
Protocol version identifier:	2.0
Date of last version of protocol:	10June2022
PASS:	No
EU PAS register number:	EUPAS45682
Active substance:	A10BK03 Empagliflozin
Medicinal product:	Jardiance®
Product reference:	NA
Research question and objectives:	
The primary objective of this research study is to determine the cardiovascular and renal effectiveness and safety of empagliflozin compared to dipeptidyl peptidate-4 inhibitor (DPP4i) in patients with T2D in the
 
 1. Overall cohort, 2. Patients with established kidney disease (DKD cohort), and 3. Patients without established kidney disease (non-DKD cohort).

Proprietary confidential information © 2023 Boehringer Ingelheim International GmbH or one or more of its affiliated companies

	The secondary objective of this research study is to determine the cardiovascular and renal effectiveness and safety of any sodium glucose co-transporter-2 inhibitors (SGLT2i) compared to glucagon-like peptide-1 receptor agonists (GLP1RA) in patients with T2D, overall and by DKD status.
Country(-ies) of study:	United States of America
Author:	
Marketing authorisation holder(s):	Boehringer Ingelheim International GmbH
Date:	26 May 2023
Page 1 of 49	
Proprietary confidential information © 2023 Boehringer Ingelheim Group of companies. All rights reserved. This document may not - in full or in part - be passed on, reproduced, published or otherwise used without prior written permission	

2. LIST OF ABBREVIATIONS

ACD	All-Cause Death
ADR	Adverse Drug Reaction
AE	Adverse Event
AESI	Adverse Event of Special interest
AKI	Acute Kidney Injury
ASMD	Absolute Standardized Mean Difference
AT	As-Treated
BI	Boehringer Ingelheim
CA	Competent Authority
CCDS	Company Core Data Sheet
CDM	Common Data Model
CI	Confidence Interval
CML	Local Clinical Monitor
CRA	Clinical Research Associate
CRF	Case Report Form
CTCAE	Common Terminology Criteria for Adverse Events
CTP	Clinical Trial Protocol
CV	Cardiovascular
DKD	Diabetic Kidney Disease
DMRP	Data Management and Review Plan
DPP4i	Dipeptidyl Peptidase-4 inhibitor
eCRF	Electronic Case Report Form
ED	Emergency Department
EHR	Electronic Health Record
ENCePP	European Network of Centres for Pharmacoepidemiology and Pharmacovigilance
ESRD/ESKD	End Stage Renal (Kidney) Disease
FDA	Food and Drug Administration
GCP	Good Clinical Practice
GEP	Good Epidemiological Practice

GLP1RA	Glucagon-like Peptide-1 Receptor Agonists
GPP	Good Pharmacoepidemiology Practice
GVP	Good Pharmacovigilance Practices
HF	Heart Failure
HR	Hazard Ratio
IB	Investigator's Brochure
IEC	Independent Ethics Committee
IQR	Interquartile Range
IRB	Institutional Review Board
ITT	Intent-to-treat
MAH	Marketing Authorization Holder
MedDRA	Medical Dictionary for Regulatory Activities
NIS	Non-Interventional Study
PASS	Post-Authorization Safety Study
PCORnet	Patient Centered Outcomes Research Network
PS	Propensity Score
QC	Quality Control
SAE	Serious Adverse Event
SEAP	Statistical and Epidemiological Analysis Plan
SGLT2i	Sodium glucose co-transporter-2 inhibitors
SOP	Standard Operating Procedure
SSDC	Study Specific Data Characterization
T1D	Type 1 Diabetes Mellitus
T2D	Type 2 Diabetes Mellitus
UTI	Urinary Tract Infection

4. ABSTRACT

Name of company: Boehringer Ingelheim			
Name of finished medicinal product: Jardiance®			
Name of active ingredient: A10BK03 Empagliflozin			
Protocol date: 26 May 2023	Study number: 1245-0228	Version/Revision: 2.0	Version/Revision date: 26 May 2023
Title of study:	Comparative cardiovascular and renal effectiveness and safety of Empagliflozin and other sodium glucose co-transporter-2 inhibitors in patients with type 2 diabetes with and without baseline kidney disease in the United States		
Rationale and background:	
While clear renal and cardiovascular (CV) benefits of empagliflozin have been demonstrated in randomized clinical trials [P15-09840], the effectiveness of this therapy in direct comparison to other anti-hyperglycemic therapies has not been shown among patients with diabetic kidney disease (DKD). Understanding the real-world clinical impact of empagliflozin in this high-risk population is critical to elucidate this medication's effect on clinical care and outcomes. Overall, we aim to use a large, national network of electronic health record (EHR) data to determine the following in a real-world population:
 
 1) Characteristics of patients with T2D, both with and without DKD, who have been initiated on empagliflozin or any sodium glucose co-transporter-2 inhibitors (SGLT2i) compared to those who have been initiated on dipeptidyl peptidase-4 inhibitor (DPP4i) or glucagon-like peptide-1 receptor agonists¹ (GLP1RA) 2) Renal and CV effectiveness of empagliflozin compared with DPP4i and SGLT2i compared with GLP1RA evaluated up to 24 months after treatment initiation 3) Safety of empagliflozin compared with DPP4i and any SGLT2i compared to GLP1RA evaluated up to 24 months after treatment initiation 		
Research question and objectives:	
The primary objective of this research study is to determine the cardiovascular and renal effectiveness and safety up to 24 months after initiation of empagliflozin compared to DPP4i in patients with T2D in the
 
 1. Overall cohort, 2. Patients with established kidney disease (DKD cohort) at baseline, and 3. Patients without established kidney disease at baseline (non- 		

Name of company: Boehringer Ingelheim			
Name of finished medicinal product: Jardiance®			
Name of active ingredient: A10BK03 Empagliflozin			
Protocol date: 26 May 2023	Study number: 1245-0228	Version/Revision: 2.0	Version/Revision date: 26 May 2023
DKD cohort).			
Study design:	
This will be a non-interventional study (NIS) using existing data from 20+ US health systems that have mapped their EHR data to the PCORnet Common Data Model [R21-4494]. The study period will be from 1 Jan 2014 through 31 December 2021, which includes data after the start of the COVID-19 pandemic. There will be an assessment of COVID-era data for quality purposes and a sensitivity analysis excluding data from March 2020 (the assumed beginning of COVID in the US) to the end of study period will be performed.
 
The primary aim of the study will include patients with T2D who initiate use of empagliflozin or DPP4i without prior use of either drug [class]. The analyses of all outcomes will compare patients with T2D initiating empagliflozin to patients with T2D initiating DPP4i.
 
The secondary aim of the study will be to examine cardiovascular and renal effectiveness and safety associated with initiation of any SGLT2i compared to GLP1RA in patients with T2D who initiate treatment without prior use of either drug class.
		
Population:	
The analysis will include adults (≥ 18 years) with T2D with or without kidney disease in the US. To study real-world treatment patterns, the study population will include a broad spectrum of patients initiating empagliflozin or any SGLT2i, DPP4i or GLP1RA. The following inclusion and exclusion criteria will be used for each two-arm comparison:
 
Inclusion criteria:
 
 - Patients ≥ 18 years old, - Having a diagnosis of T2D within 12 months prior to the index date based on ICD-9 and -10 codes and other available data, - Record of 1+ prescription for empagliflozin, any SGLT2i, any DPP4 inhibitor, or any GLP1RA use between 1 January 2015 and 31 December 2020, and - No record of any prescription for the drugs being compared 		

Name of company: Boehringer Ingelheim			
Name of finished medicinal product: Jardiance®			
Name of active ingredient: A10BK03 Empagliflozin			
Protocol date: 26 May 2023	Study number: 1245-0228	Version/Revision: 2.0	Version/Revision date: 26 May 2023
		
during the 12 months preceding the index date, i.e.,
 
 ○ For the primary comparison of initiation of empagliflozin versus DPP4 inhibitors, patients will not have any prescription for empagliflozin/any SGLT2i or DPP4 inhibitors during the preceding 12 months. ○ For the comparison of initiation of SGLT2i versus GLP1RA, patients will not have any prescription for SGLT2i or GLP1RA during the preceding 12 months. 
Exclusion criteria:
 
 - Aged <18 years on the first prescription date of the qualifying prescription, - Pre-existing diagnosis of Type 1 diabetes (T1D) during the 12 months before the index date, - Having a disqualifying diagnosis during the 12 months before the index date, defined as having at least one of the following: estimated glomerular filtration rate (eGFR) <30, dialysis, polycystic kidney disease or a kidney transplant, - <12 months of available data before the index date, and/or no complete history of drug prescriptions/or other records of drug use during this period, defined as not having at least 1 ambulatory visit and at least 1 medication prescription during the preceding 12 months, and - Missing or ambiguous data on serum creatinine in the preceding 12 months. 	
Variables:		
Exposure variables will include:
 
 ● Initiation of empagliflozin, GLP1RA, DPP4 inhibitors or any SGLT2i for the treatment of T2D 
Outcomes (evaluated through 24 months after index date):
 
Primary effectiveness outcomes:
 
 ● Composite of a 40% decline in eGFR, incident ESRD, or all-cause death (ACD) 	

Name of company: Boehringer Ingelheim			
Name of finished medicinal product: Jardiance®			
Name of active ingredient: A10BK03 Empagliflozin			
Protocol date: 26 May 2023	Study number: 1245-0228	Version/Revision: 2.0	Version/Revision date: 26 May 2023

Secondary effectiveness outcomes:
 
 • Individual renal events: 40% decline in eGFR, incident ESRD, dialysis, and kidney transplant • Hospitalizations for cardiovascular events: heart failure (HF), HF+ACD, myocardial infarction+stroke+coronary revascularization+ACD, myocardial infarction+stroke+ACD • ACD 
Secondary safety outcomes:
 
 • Diabetic ketoacidosis • Severe hypoglycaemia • Urinary tract cancer • Acute kidney injury (AKI) that requires dialysis • Genital mycotic infection • Severe urinary tract infections 
Covariates: Several baseline patient characteristics will be captured in the 12 months prior to the index date. Covariates that will be included as covariates in the propensity scores (PS) model include (not are not limited to):
 
 • Demographics (age, sex, race/ethnicity, BMI, quarter and year of incident prescription, smoking status) • Comorbidities: history of heart failure, history of CV events (MI, stroke, PCI, CABG, PAD), hypertension • Prior/concomitant use of other glucose lowering agents • Prior/concomitant use of other medications e.g., cardiovascular agents (ACE/ARB, beta blocker, ARNi, statin) and diuretics • Relevant lab test results, e.g., eGFR, HbA1c, HDL-c, etc. 
Note: See Section 9.3.3 for complete list of covariates
			
Data sources:		This study will utilize high-quality renal function laboratory data available in medical electronic health records from approximately 20	

Name of company: Boehringer Ingelheim			
Name of finished medicinal product: Jardiance®			
Name of active ingredient: A10BK03 Empagliflozin			
Protocol date: 26 May 2023	Study number: 1245-0228	Version/Revision: 2.0	Version/Revision date: 26 May 2023
	
health systems in the US that have mapped their data to the PCORnet Common Data Model (CDM). Sites meeting PCORnet data curation quality checks will be eligible to participate in this study. Sites will be approached for participation in this study based on an initial feasibility assessment to determine the extent and completeness of key data elements (renal laboratory data, prescription data, relevant medical diagnoses, and data from both inpatient and outpatient encounters). Death data will be ascertained from site records and augmented with de-identified encrypted linkage to external sources, which includes reported deaths from the government and commercial obituaries using Datavant Software.
		
Study size:	
A sample size of N=7,600 per group with median follow-up duration of 18 months will provide 80% power to detect a hazard ratio of 0.80, assuming an incidence rate of 30 per 1,000 patient years for the primary composite renal outcome in the reference cohort.
		
Data analysis:	
The index date in this study is defined as the date of the first recorded order for a qualifying prescription as a new user. Patients are required to have at least 1 ambulatory visit and at least 1 medication prescription in the 12 months prior to initiation of empagliflozin or a comparator drug (the look-back period). The look-back period includes the index date. The main analyses of this study will utilize a modified As-Treated (AT) approach and an Intention-to-Treat (ITT) approach will be used as a sensitivity analysis for the primary and secondary comparisons of the primary outcome.
 
Follow-up starts from the day after the index date until the first qualifying event has been met:
 
 • First occurrence of outcome of interest • Death • 2 years following the index prescription • End of query specific study period (December 31, 2021) • Empagliflozin user starts a DPP4i or other type of SGLT2i, or if a DPP4i user starts any SGLT2i 
 ○ SGLT2i user starts a GLP1RA, or a GLP1RA user starts any SGLT2i 		

Name of company: Boehringer Ingelheim			
Name of finished medicinal product: Jardiance®			
Name of active ingredient: A10BK03 Empagliflozin			
Protocol date: 26 May 2023	Study number: 1245-0228	Version/Revision: 2.0	Version/Revision date: 26 May 2023

 No observed prescriptions for the index drug within 1 year (+30 days) from the last observed prescription 
The primary analysis will be performed using overlap weighting to balance covariates across the two treatment arms (empagliflozin vs DPP4i) and Cox proportional hazards modelling to determine the effect of drug on outcomes. To create the overlap weights, the following will be performed:
 
For each two-arm study comparison and within the DKD and non-DKD subgroups separately, propensity score models will be built using a logistic LASSO model with the covariates of interest and all subgroup by covariate pairwise interactions. The outcome of interest is treatment group, with empagliflozin [or any SGT2i] as the treatment of interest and DPP4i [or GLP1RA] as the reference group. The variables/interactions that are remaining in the LASSO model are refit to a standard logistic regression and the resulting predicted probability for each patient is considered the PS. For patients on the reference treatment, the overlap weight is the same as the PS. For patients on the treatment of interest, the overlap weight is 1-PS. No trimming is required due to the PS weights being bounded between 0 and 1. Distributions of covariates in the DKD and non- DKD groups and further within subgroups of interest will be assessed using standardized mean differences. Absolute standardized mean differences will be visually depicted using the CONNECT-S plot.
 
For each outcome, incidence rates (number of events per 1000 PY of follow-up), hazard ratios, and corresponding 95% confidence intervals (CI) will be presented. Hazard ratios and CI will be calculated using weighted Cox proportional hazards models. For the AT analysis, if an empagliflozin or DPP4i user initiates a GLP1RA during the follow-up period, this will be adjusted for in the comparison of empagliflozin and DPP4i (and similarly for users initiating a DPP4i).
 
Analyses will be performed overall and within DKD subgroups. A sensitivity analysis will be performed using propensity score
			

Proprietary confidential information © 2023 Boehringer Ingelheim International GmbH or one or more of its affiliated companies

Name of company: Boehringer Ingelheim			
Name of finished medicinal product: Jardiance®			
Name of active ingredient: A10BK03 Empagliflozin			
Protocol date: 26 May 2023	Study number: 1245-0228	Version/Revision: 2.0	Version/Revision date: 26 May 2023
	
matching in place of overlap weighting.
 
Another sensitivity analysis will be performed excluding data available from March 2020 to the end of the study period to reduce the impact of the pandemic.
 
A sensitivity analysis for the primary efficacy comparison will be performed where eGFR decline requires ≥ 1 measurement during follow-up (instead of ≥ 2).
 
Given this is a retrospective study utilizing EHR data from multiple sites, the protocol-specified analyses may need to be modified based on overall data collection completeness (data latency) and final cohort sample sizes.
		
Milestones:	
 - Final protocol and SEAP: Q2 2022 - ENCEPP registration: After finalization of the study protocol (Q2 2022) - Contracts executed with sites: Q1 2022 - Data collection via distributed query: Q2 2022 - Final report: Q4 2023 - Manuscript submission: Q4 2023 		

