9.2.2.1 Inclusion criteria

Inclusion criteria:

- Patients ≥ 18 years old,
- Having a diagnosis of type 2 diabetes in 12 months before the index date (defined as the date of initiation of empagliflozin or GLP1RA or DPP4i, based on the cohort evaluated), based on ICD-9 and -10 codes and other available data (see SEAP for details),
- Record of prescription for empagliflozin, any SGLT2i, any DPP4 inhibitor, or any GLP1RA use between 1 January 2015 and 31 December 2020, and
- No record of any prescription for the drugs being compared during the 12 months + 30-day grace preceding the index date period, i.e.,
 - o For the primary comparison of initiation of empagliflozin versus DPP4i, patients will not have any prescription for empagliflozin/any SGLT2i or DPP4i during the preceding 12 months + 30-day grace period.
 - o For the comparison of initiation of SGLT2i versus GLP1RA, patients will not have any prescription for SGLT2i or GLP1RA during the preceding 12 months + 30-day grace period.

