9.2.2.2 Exclusion criteria

Exclusion criteria:

- Aged < 18 years on the first prescription date of the qualifying prescription,
- Pre-existing diagnosis of T1DM during the 12 months before the index date,
- Having a disqualifying diagnosis during the 12 months before the index date, defined as having at least one of the following: eGFR < 30 , dialysis, polycystic kidney disease or a kidney transplant,
- < 12 months of available data before the index date, and/or no complete history of drug dispensations/other records of drug use during this period, defined as not having at least 1 ambulatory visit and at least 1 medication prescription during the preceding 12 months, and
- Missing or ambiguous data on serum creatinine in the 12 months prior to the index date or sex.

[figure not shown]

Figure 1 Consort diagram of study population, the application of inclusion and exclusion criteria, and the resulting study cohorts

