9.6 DATA MANAGEMENT

The data will be extracted through standardized SAS queries that are distributed to health systems and executed against the most recently approved PCORnet CDM. Data will be delivered to [REDACTED] via secure shared Box folders and linked to death data using Datavant Software. All analyses will be performed using SAS v9.4 or R. Only individuals on the IRB for this project will have access to the data, and it will all be stored on secure servers behind the [REDACTED] firewall.

Missing data (e.g., for demographics, vital signs, lab measures) will be documented to report extent of missingness. Missing data will be excluded from denominators in descriptive summaries. For regression models, extent of missing covariate data will be evaluated and appropriate measures for covariates will be taken. This may include multiple imputation or defining the covariate differently, when possible.

For diagnoses, procedures and medications, absence of a relevant code during the specified time window will be interpreted as 'no evidence'. For these factors we hope to avoid possible

misclassification through appropriate eligibility criteria (e.g., restricting to patients with evidence of interaction within the health system). For time-to-event analyses, follow-up will be censored early if patient has lost contact with the health system (defined as 18 months after last encounter with the health system).

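### The Abstract counts the index date in the look-back, so the test for 12 months of prior data can be met with no earlier visit or prescription; the eligibility sections are worded otherwise

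*Protocol*

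**What the plan says.** **Abstract, Data analysis.** The index date is fixed first: "The index date in this study is defined as the date of the first recorded order for a qualifying prescription as a new user". The prior-data requirement follows: "Patients are required to have at least 1 ambulatory visit and at least 1 medication prescription in the 12 months prior to initiation". That window is labelled the look-back period, and the next sentence reads "The look-back period includes the index date". This sentence appears nowhere else in the Protocol.

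**Exclusion criteria.** The Abstract excludes patients with "<12 months of available data before the index date". Section 9.2.2.2 has the matching item: "months of available data before the index date, and/or no complete history of drug dispensations/other records of drug use during this period". Both turn it into a working rule in the same way: "defined as not having at least 1 ambulatory visit and at least 1 medication prescription during the preceding 12 months". No minimum interval between the first record and the index date is given.

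**Other windows.** Section 9.2.2.1 places the type 2 diabetes diagnosis in the 12 months before index, and Section 9.2.2.2 does the same for serum creatinine. The new-user washout is "No record of any prescription for the drugs being compared during the 12 months + 30-day grace preceding the index date period". In Section 9.2.3 the Figure 2 caption describes the look-back as pre-index. Table 1 separates the prior year from baseline and ticks medical history only under the prior year. The same section, however, draws baseline data from the baseline encounter as well, and Section 9.3.1 defines kidney disease status partly from the index encounter.

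**Section 9.6.** A missing diagnosis, procedure or medication code is taken as lack of evidence for that item. The stated protection against misclassification is eligibility, for example "restricting to patients with evidence of interaction within the health system".

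**The concern.** A new-user design depends on the period before the index date having been observed. Here exposure is known only from written orders, without claims or fill data (Section 9.3.1), and Section 9.9 concedes that data generated in another health system may be missing. A patient who moves into a participating system already taking the drug will have a first recorded order there and will look like an initiator, unless eligibility demands some earlier contact.

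The visit-and-prescription rule is the Protocol's only test of that contact. If the index encounter itself can satisfy it, two things are at stake:

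- **New-user status.** An empty record passes the washout whether the patient was untreated or was treated elsewhere.
- **Covariates.** Section 9.6 reads absent codes as lack of evidence and relies on eligibility to make that reasonable. Standardized differences compare recorded values only, so they cannot show that a history was never observed.

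The intention-to-treat, propensity-matching, COVID-period and single-eGFR sensitivity analyses described in the Protocol do not address either problem.

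**Working it through.** No sample size, event count or error rate enters this point, so there is no figure to reproduce. The check takes a hypothetical patient through each rule under both readings.

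**Inputs:** the index date, the visit-and-prescription rule and the look-back boundary (Abstract, Data analysis); the exclusion for insufficient data (Abstract and Section 9.2.2.2); the diagnosis and washout windows (Section 9.2.2.1); the creatinine window (Section 9.2.2.2).

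**Patient A: every record (visit, diabetes code, creatinine, order) falls on the index date.**

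| Criterion | Index date inside the look-back | Index date outside the look-back |
|---|---|---|
| At least 1 prescription | Met by the index order, for every patient | Fails |
| At least 1 ambulatory visit | Met if the order was written at an ambulatory visit | Fails |
| Diabetes diagnosis | Met only if the inclusive rule extends to this window | Fails |
| Serum creatinine | Met only if the inclusive rule extends to this window | Fails |
| Washout | Passes, as no earlier order is on record | Passes |

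**Patient B: a diabetes code and a creatinine value from an inpatient stay before index, but no earlier ambulatory visit or prescription on record.** Patient B shows what follows if the inclusive sentence governs only the rule it is attached to. The diagnosis and creatinine criteria are met on their pre-index wording. The prescription half is met by the index order, and the visit half by an ambulatory index visit. Patient B enters under the Abstract. With pre-index wording throughout, Patient B is excluded.

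**What follows**

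1. With the index date counted, the prescription half excludes nobody, because an index date cannot exist without an order on that date.
2. The visit half then excludes only patients whose index order was not accompanied by an ambulatory visit and who had none earlier.
3. No other test of 12 months of available data is given, so that exclusion can be passed with no earlier visit or prescription on record.
4. The inclusive rule cannot hold for every window. Applied to the washout, the index order would disqualify every patient. The sentence must therefore be limited to some criteria, and the Protocol does not say which.

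**The case against.** The strongest reply is that the inclusive sentence occurs once, in the Abstract, and that the criteria themselves are worded as preceding the index date. On that wording a patient with no earlier record fails on visit, prescription, diagnosis and creatinine. The sentence may be meant only for capturing baseline covariates, since Section 9.2.3 also uses the baseline encounter. The limitations section acknowledges data held elsewhere. The first analysis phase (Section 9.7.1) and the data characterization query (Section 9.8) allow the issue to be noticed before outcomes are compared, and the analysis plan, which is not at hand, may settle the rule.

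Much of this stands. It shows that the lax rule is not the settled effect of the Protocol. It does not remove the contradiction: the sentence directly follows the visit-and-prescription rule and refers to the window that rule has just named. None of the later checks changes the eligibility wording.

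A reader might go further and infer three things that the documents do not support:

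- **That patients with no earlier record do enter as new users.** This holds only if the Abstract governs, the index order comes with an ambulatory visit, and the diagnosis and creatinine windows also admit the index date, which their wording does not say.
- **That the criterion excludes almost nobody.** No count in the Protocol bears on this.
- **That affected patients have entirely empty histories.** Same-day records can populate some covariates, so their histories may be sparse rather than empty.

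A separate point holds on either reading: one visit and one prescription a week before index would suffice, so the washout need not be fully observable. Requiring longer contact is a trade-off against cohort size and representativeness, and it would not prove non-use elsewhere. It is not an error in the Protocol.

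**Conclusion.** The Protocol contradicts itself on whether index-date records count toward the prior-data requirement. Under the Abstract's rule, the only operational test of 12 months of available data can be met without any earlier visit or prescription. That opens a route for patients treated elsewhere to enter as new users and weakens the safeguard on which Section 9.6 depends.

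The contradiction rests on the text alone. The consequence rests on the Abstract's rule being the one programmed and, for the visit half, on an ambulatory visit on the index date. The number of patients affected, and the direction and size of any effect on the hazard ratio, cannot be derived from the documents. The point bears on both comparisons, because the same criteria apply to each.

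**What to change.** 1. State for each criterion (visit, prescription, diabetes diagnosis, creatinine, kidney disease status, covariates, washout) whether index-date records count, and make the Abstract and Sections 9.2.2 and 9.2.3 agree.
2. For the data-availability exclusion, require the qualifying ambulatory visit, and at least one prescription other than the index order, to fall strictly before the index date.
3. Count by arm how many patients this removes, and report the counts before the comparative analysis. Section 5 shows that first-phase analyses have been run, so this should be a filter on data already in hand, provided the extract carries visit and order dates.
4. Optionally, add a sensitivity analysis restricted to patients with a recorded encounter early enough for the washout of 12 months plus 30 days to be observable. This need not become an eligibility criterion.

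The cost is a wording amendment, a query filter and a somewhat smaller cohort. If the queries already use the pre-index rule, only the Abstract sentence needs correcting and no patients are lost.
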